7.6.4.1 Primary Efficacy Endpoint and Analysis

The primary clinical efficacy analysis will be the change from baseline in UEC score for the SA-ER group compared with placebo based on bilateral strength recorded in the following muscle groups using a dynamometer: gross grip, shoulder abductors, elbow flexors, and elbow extensors. The UEC is derived from the sum of the muscle groups. Each muscle group value will represent the average of the right and left total values (measured in kg).

The comparison of the two treatment groups will be based on the change from baseline in mean UEC score between SA-ER and placebo using GEE repeated measures analysis with baseline, gender, and geographic region as covariates. Region is considered as a covariate to account for the heterogeneity of the disease observed in some European countries and Israel relative to North American patients.

For missing assessments for an individual subject, these data would remain as missing or will be imputed based on the rules provided in the SAP. For those subjects who are in the study for some period of time but decline in function and leave the study, regardless of whether that is the reason listed for withdrawal, the GEE method might not adequately cover the projected decline for these subjects and may not be appropriately conservative. In such cases a single imputation method will be used to estimate the change in strength over the remaining time of the study using the existing subject's data and these imputed values will be used for the GEE analysis.

Details on primary endpoint analysis will be fully delineated in the SAP.

7.6.4.2 Secondary Endpoints and Analyses

Analyses of secondary efficacy endpoints will follow the same methods as the primary analyses of the primary endpoint, where data are available. Additional details on the analysis of secondary endpoints will be described in the SAP.

7.6.4.2.1 Key Secondary Endpoints

The key secondary clinical efficacy analyses will assess the change from baseline for the SA-ER group compared with the placebo group using GEE for the following variables:

- LEC score based on a sum of the mean bilateral strength recorded in the following muscle groups: knee flexors, hip flexors, hip extensors, hip abductors and hip adductors

- Muscle strength in the knee extensors: bilateral total force (measured in kg)
- GNEM-FAS mobility domain score

Hochberg's adjustment for multiplicity (Hochberg 1988) will be used for the key secondary endpoints, specifically LEC score, knee extensor strength, and GNEM-FAS mobility domain score.

7.6.4.2.2 Other Secondary Endpoints

The analysis of other secondary endpoints will assess the change from baseline for the SA-ER group compared to the placebo group using GEE for the following variables:

- GNEM-FAS upper extremity domain score
- Sit-to-stand score calculated as the number of times a subject can rise from a sitting to a standing position in a 30-second period
- Weighted arm lift score calculated as the number of times a subject can raise a 1 kg weight overhead in a 30-second period
- Walking ability as measured by the 6MWT, which will be reported as distance in meters and percent predicted based on normative data for age and gender.

7.6.4.3 Tertiary Endpoints and Analysis

Analyses of tertiary endpoints will follow the same methods as the primary analyses of the primary endpoint, where data are available. The tertiary clinical efficacy analyses will assess the change from baseline for the SA-ER group compared to the placebo group using GEE for the following endpoints:

- UEC score based on percent predicted bilateral strength recorded in the upper extremity muscle groups
- LEC score based on percent predicted bilateral strength recorded in the upper extremity muscle groups
- Muscle strength (total force in kg) for each individual muscle group comprising the UEC and LEC
- Percent predicted muscle strength for each individual muscle group comprising the UEC and LEC using published normative data adjusted for age, gender, and weight
- Percent of predicted muscle strength in the knee extensors using published normative data adjusted for age, gender, and weight
- GNEM-FAS total score
- GNEM-FAS self-care domain score

- Health-related quality of life as measured by the INQoL, which will be reported as subscale scores with higher scores associated with more significantly diminished quality of life
- CGI-I scores
- CK levels in serum
- Trough (pre-dose) SA levels in serum (free) and urine (free, total, and bound; corrected for creatinine)

Additional details on the analysis of tertiary endpoints will be described in the SAP.

7.6.5 Analyses of Drug Concentration Measurements

The SA analysis set will be used to evaluate free serum SA levels and urine SA levels (free, bound and total; corrected for creatinine) at trough (pre-dose). Changes from baseline will be analyzed using repeated measures analysis. The comparison will be between the SA-ER treatment group and placebo group using GEE.

7.6.6 Safety Analyses

The safety analysis set will be used for the analyses of all safety endpoints (Section 7.6.3). Safety will be evaluated by the incidence, frequency and severity of AEs and SAEs, including clinically significant changes from study baseline to scheduled time points in:

- Interval history
- Vital signs
- Physical examination findings
- Clinical laboratory evaluations
- Suicidal ideation and behavior assessments
- Concomitant medications

All AEs will be coded using the Medical Dictionary for Regulatory Activities (MedDRA). The incidence and frequency of AEs will be summarized by System Organ Class (SOC), Preferred Term (PT), severity, and relationship to treatment. The numbers (frequency) and incidence rates of AEs and SAEs will be summarized by treatment group. A by-subject listing will be provided for those subjects who experience a SAE, including death, or experience an AE associated with early withdrawal from the study or study drug treatment.

Clinical laboratory data will be summarized by the type of laboratory test. The frequency and percentage of subjects who experience abnormal clinical laboratory results (i.e. outside of reference ranges) and/or clinically significant abnormalities will be presented for each clinical laboratory measurement. For each clinical laboratory measurement, descriptive

statistics will be provided for study baseline and all subsequent post-treatment scheduled visits. Changes from study baseline to the post-treatment visits will also be provided.

Changes in findings from study baseline physical examinations will be tabulated for each subject by examination category. If there are examination findings that change in more than one subject, these will be tabulated in a separate table and expressed as the number of subjects with the change out of the total. No statistics will be applied to the physical examination findings.

The SAP will provide additional details on the planned safety analyses.

7.6.7 Data Monitoring Committee

An independent DMC with appropriate expertise in the conduct of clinical trials will act in an advisory capacity to monitor subject safety on a routine basis throughout the trial. A review of blinded safety data will be conducted by the DMC at least two times a year, with the first meeting scheduled once the first subject has been enrolled. Ad hoc meetings will be held if indicated based on observed events. The responsibilities of the DMC will be fully defined in a DMC charter.

8 STUDY CONDUCT

8.1 Ethics

8.1.1 Institutional Review Board or Ethics Committee

The IRB/Ethics Committee (EC) must be a properly constituted board or committee operating in accordance with 21 CFR Part 56, "Institutional Review Boards." This protocol, any protocol amendments, and the associated informed consent forms (ICFs) must be submitted to the IRB/EC for review and must be approved before screening of any subject into the study. Study drug may not be shipped to the Investigator until Ultragenyx or its designee has received a copy of the letter or certificate of approval from the IRB/EC for the protocol and any protocol amendments, as applicable.

All subject recruitment and/or advertising information must be submitted to the IRB/EC and Ultragenyx or its designee for review and approval prior to implementation. IRB/EC approval of any protocol amendments must be received before any of the changes outlined in the amendments are put into effect, except when the amendment has been enacted to protect subject safety. In such cases, the chair of the IRB/EC should be notified immediately and the amendment forwarded to the IRB/EC for review and approval.

8.1.2 Ethical Conduct of Study

This protocol is written in accordance with the principles established by the 18th World Medical Association General Assembly (Helsinki, 1964) and subsequent amendments and clarifications adopted by the General Assemblies. The Investigator will make every effort to assure the study described in this protocol is conducted in full conformance with those principles, current FDA regulations, ICH Good Clinical Practices (GCP) guidelines, and local ethical and regulatory requirements. Should a conflict arise, the Investigator will follow whichever law or guideline affords the greater protection to the individual subject. The Investigator will also make sure he or she is thoroughly familiar with the appropriate administration and potential risks of administration of the study drug, as described in this protocol and the IB, prior to the initiation of the study.

8.1.3 Subject Information and Consent

Appropriate forms for documenting written informed consent will be provided by the Investigator and reviewed and approved by Ultragenyx or its designee before submission to the IRB/EC. Ultragenyx or its designee must receive a copy of the IRB/EC's approval of the ICF before the shipment of study drug to the study site.

It is the Investigator's responsibility to obtain signed written informed consent from each potential study subject prior to the conduct of any study procedures. This written informed consent will be obtained after the methods, objectives, requirements, and potential risks of the study have been fully explained to each potential subject. The Investigator must explain to each subject that the subject is completely free to refuse to enter the study or to withdraw from it at any time.

The method of obtaining and documenting informed consent and the contents of the ICF will comply with ICH GCP guidelines, the requirements of 21 CFR Part 50, "Protection of Human Subjects," the Health Insurance Portability and Accountability Act (HIPAA) regulations, and all other applicable regulatory requirements. Subjects will be given a copy of the signed ICF and will be provided any new information during the course of the study that might affect their continued participation in the study. The Investigator or a qualified designee will be available to answer each subject's questions throughout the study, and all of the subject's questions must be answered to the subject's satisfaction. If the protocol is amended and the ICF is revised, each subject will be required to provide written informed consent again using the revised ICF.

The date of written informed consent will be documented in each potential subject's CRF. The signed ICF will remain in each subject's study file and must be available to the study monitor(s) at all times.

8.2 Investigators and Study Administrative Structure

Each Investigator must provide Ultragenyx and/or its designee a completed and signed Form FDA 1572 and a Financial Disclosure Form. All sub-investigators must be listed on Form FDA 1572 and Financial Disclosure Forms must be completed for all sub-investigators listed on Form FDA 1572.

Ultragenyx and/or its designee will be responsible for managing and monitoring the clinical trial to ensure compliance with FDA and ICH GCP guidelines. Ultragenyx's trained designated representative (the monitor) will conduct regular visits to the clinical site to perform source document verification. The monitor will verify the Investigator's ongoing qualifications, inspect clinical site facilities, and inspect study records, including proof of IRB/EC review, with the stipulation that subject confidentiality will be maintained in accordance with local and federal regulations, including HIPAA requirements.

A Coordinating Investigator will be identified for multicenter trials. The Coordinating Investigator will be selected on the basis of active participation in the trial, thorough knowledge of the therapeutic area being studied, and the ability to interpret data. The Coordinating Investigator will read and sign the Clinical Study Report (CSR).

8.3 Investigational Product Accountability

While at the clinical site, study drug must be stored in a secure limited access location at controlled temperature as described in the IB and according to product packaging. The storage facility must be available for inspection by the study monitor at any time during the study.

A drug accountability record must be maintained for all study drug received, dispensed, returned, and/or lost during the study. This record must be kept current and made available to the study monitor for inspection. Following the close-out of the study, all unused study

drug must be returned to Ultragenyx and/or its designee unless other instructions have been provided for final disposition of the study drug.

8.4 Data Handling and Record Keeping

8.4.1 Case Report Forms and Source Documents

The Investigator is required to initiate and maintain, for each subject, an adequate and accurate case history that records all observations and other data related to the study for that subject. A validated electronic data capture (EDC) system will be used for entry of the data into electronic CRFs. Data must be recorded on CRFs approved by Ultragenyx or its designee. All information recorded on CRFs for this study must be consistent with the subject's source documentation.

Initial data entry and any changes to the data will be made only by Ultragenyx-authorized users, and data entries and changes will be captured in an electronic audit trail.

An explanation of any data change should be recorded in the CRF. All data entered in to the CRF must be verifiable; therefore, CRFs will be routinely checked for accuracy, completeness, and clarity and will be cross-checked for consistency with source documents, including laboratory test reports and other subject records by Ultragenyx or its designee. The Investigator must allow direct access to all source documents.

8.4.2 Data Quality Assurance

Monitoring and auditing procedures developed by Ultragenyx and/or its designee will be implemented to ensure compliance with FDA and ICH GCP guidelines. Ultragenyx's designated representative (the monitor) will contact the Investigator and conduct regular visits to the study site. The monitor will be expected and allowed to verify the Investigator's qualifications, to inspect clinical site facilities, and to inspect study records, including proof of IRB/EC review, with the stipulation that subject confidentiality will be maintained in accordance with local and federal regulations, including HIPAA requirements. The monitor will also be responsible for confirming adherence to the study protocol, inspecting CRFs and source documents, and ensuring the integrity of the data. CRFs will be checked for accuracy, completeness, and clarity and will be cross-checked for consistency with source documents including progress notes, laboratory test reports and other subject records. Instances of missing or uninterruptable data will be resolved in coordination with the Investigator.

The monitor will also investigate any questions concerning adherence to regulatory requirements. Any administrative concerns will be clarified and followed. The monitor will maintain contact with the site through frequent direct communications via e-mail, telephone, facsimile, and/or mail. The Investigator and all other site personnel agree to cooperate fully with the monitor and will work in good faith with the monitor to resolve any and all questions raised and any and all issues identified by the monitor.

The Investigator understands that regulatory authorities, the IRB/EC, and/or Ultragenyx or its designees have the right to access all CRFs, source documents, and other study

documentation for on-site audit or inspection and will retain this right from the start of the study to at least two years after the last approval of a marketing application or for at least two years after clinical development of the study drug for the indication being studied has been discontinued. The Investigator is required to guaranty access to these documents and to cooperate with and support such audits and inspections.

8.4.3 Record Retention

All study records must be retained for at least two years after the last approval of a marketing application in the US or an ICH region and until: 1) there are no pending or contemplated marketing applications in the US or an ICH region, or 2) at least two years have elapsed since the formal discontinuation of clinical development of the investigational product under study. The Investigator/institution should retain subject identifiers for at least 15 years after the completion or discontinuation of the study. Subject files and other source data must be kept for the maximum period of time permitted by the hospital, institution or private practice, but not less than 15 years. These documents should be retained for a longer period, however, if required by the applicable regulatory requirements or by an Ultragenyx agreement. Ultragenyx must be notified and will assist with retention should the Investigator/institution be unable to continue maintenance of subject files for the full 15 years. All study records must be stored in a secure and safe facility.

8.5 Reporting and Follow-up of Adverse Events

8.5.1 Definition of Adverse Events

An AE is defined as any untoward medical occurrence associated with the use of a drug in humans, whether or not considered drug related. An AE can therefore be any unfavorable and unintended sign (including an abnormal laboratory finding, for example), symptom, or disease temporally associated with the use of a medicinal (investigational) product, whether or not related to the medicinal (investigational) products.

A suspected adverse reaction is any AE for which there is a reasonable possibility that the drug caused the AE. For the purposes of expedited safety reporting, “reasonable possibility” means there is evidence to suggest a causal relationship between the drug and the AE. Suspected adverse reaction implies a lesser degree of certainty about causality than adverse reaction, which means any AE caused by a drug.

Life-threatening AE or life-threatening suspected adverse reaction is an AE or suspected adverse reaction that, in the view of either the Investigator or Ultragenyx, places the patient or subject at immediate risk of death. It does not include an AE or suspected adverse reaction that, had it occurred in a more severe form, might have caused death.

An AE or suspected adverse reaction is considered “unexpected” if it is not listed in the current Investigators Brochure’s Reference Safety Information (RSI) or is not listed at the specificity or severity that has been observed.

An SAE or serious suspected adverse reaction is an AE or suspected adverse reaction that at any dose, in the view of either the Investigator or Ultragenyx, results in any of the following outcomes:

- Death
- A life-threatening AE
- Inpatient hospitalization or prolongation of existing hospitalization
- Persistent or significant incapacity or disability (substantial disruption of the ability to conduct normal life functions)
- A congenital anomaly/birth defect

Note that hospitalizations planned prior to study enrollment (e.g. for elective surgeries) are not considered SAEs. Hospitalizations that occur for pre-existing conditions that are scheduled after study enrollment are considered SAEs.

Important medical events that may not result in death, be immediately life-threatening, or require hospitalization may be considered serious when, based upon appropriate medical judgment, they may jeopardize the patient or subject and may require medical or surgical intervention to prevent one of the outcomes listed in the definition.

8.5.2 Severity of Adverse Events

Wherever possible, the severity of all AEs will be graded using the NCI CTCAE (version 4.03). The majority of AEs can be graded using this system.

If an AE cannot be graded using the CTCAE criteria, it should be graded as mild, moderate, severe, life-threatening, or death using the following definitions.

- Mild (Grade 1): Awareness of signs or symptoms, but easily tolerated and of a minor irritant type, causing no loss of time from normal activities. Symptoms do not require therapy or a medical evaluation; signs and symptoms are transient.
- Moderate (Grade 2): Events introduce a low level of inconvenience or concern to the participant and may interfere with daily activities, but are usually improved by simple therapeutic measures; moderate experiences may cause some interference with functioning.
- Severe (Grade 3): Events interrupt the participant's normal daily activities and generally require systemic drug therapy or other treatment; they are usually incapacitating.
- Life-threatening (Grade 4): Events that place the participant at immediate risk of death or are disabling.
- Death (Grade 5): Events that result in death.

To make sure there is no confusion or misunderstanding of the difference between the terms "serious" and "severe," which are not synonymous, the following note of clarification is provided. The term "severe" is often used to describe the intensity (severity) of a specific event (as in mild, moderate, or severe myocardial infarction); the event itself, however, may be of relatively minor medical significance (such as severe headache). This is not the same as "serious" which is based on subject/event outcome or action criteria usually associated with events that pose a threat to a subject's life or functioning. Seriousness (not severity) serves as a guide for defining regulatory reporting obligations.

8.5.3 Relationship of Adverse Events to Study Drug

The Investigator will assess the potential relationship of the AE to study drug using the following descriptions.

Categories of attributions for "Unrelated" events:

- **Unrelated:** This category applies to an AE that *is clearly not related* to the investigational agent/procedure.
- **Unlikely Related:** This category applied to an AE that *is doubtfully related* to the investigational agent/procedure.

Categories of attributions for "Related" events:

- **Possibly Related:** This category applies to an AE that *may be related* to the investigational agent/procedure.
- **Probably Related:** This category applies to an AE that *is likely related* to the investigational agent/procedure.
- **Definitely Related:** This category applies to an AE that *is clearly related* to the investigational agent/procedure.

For the purposes of reporting to regulatory agencies, AEs deemed as Definitely, Probably or Possibly Related will be considered Related and those deemed Unrelated or Unlikely Related will be considered Unrelated.

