At Week 24, the UEC score showed a statistically significant difference in the 6 g/day group compared with placebo (+2.33 kg; 5.5% relative difference from baseline; $p=0.040$). At Week 48, a statistically significant difference between the combined 6 g/day group and the combined 3 g/day group was observed (+3.44 kg; 8.5% relative difference from baseline; $p=0.0033$). Subjects with less advanced disease (able to walk more than 200 meters at screening in the six-minute walk test, 6MWT), a predefined subset that comprised approximately 70% of total enrollment, showed a more pronounced difference (+4.69 kg; 9.7% relative difference from baseline; $p=0.0005$).

A similar pattern of response was observed in the LEC, but was not statistically significant between the dose groups. None of the treatment groups showed a significant decline in function. There was no significant difference (increase or decline) in the 6MWT. The GNE Myopathy Functional Activities Scale (GNEM-FAS) did not show differences at Week 24; a positive trend in total ($p=0.086$), mobility ($p=0.087$), and upper extremity scores ($p=0.096$) in the combined 6 g/day vs 3 g/day groups was observed at Week 48 when analyzed by the pre-specified ANCOVA analysis. Changes in total, mobility, and upper extremity scores were significant in the combined 6 g/day vs 3 g/day groups when analyzed in a post-hoc analysis.

SA-ER appeared to be well tolerated with no SAEs reported in either dose group and no dose-dependent TEAEs identified. Common TEAEs included headache, arthralgia, back pain, fatigue, diarrhea, influenza-like illness, musculoskeletal pain, myalgia, nasal congestion and nasopharyngitis. Most AEs were mild to moderate in severity.

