7.5.2.1 Dynamometry

Dynamometry of multiple muscle groups will be used to derive the primary efficacy endpoint as well as multiple secondary and tertiary efficacy endpoints. Dynamometry sessions will occur at each visit beginning with the Screening Visit to serve as training and ensure the subject meets eligibility criteria.

Formal training will be conducted with the clinicians administering dynamometry (preferably a licensed physical therapist) to standardize technique and minimize variability. The maximum voluntary isometric contraction (MVIC) against a dynamometer will be used to measure strength in the following muscle groups: shoulder abductors, elbow flexors, elbow extensors, hip abductors, hip adductors, hip flexors, hip extensors, knee flexors and knee extensors. A hand dynamometer will be used to assess gross grip strength.

Each effort will last approximately three seconds with a slow build to a maximum voluntary force. Strength in the elbow flexors and elbow extensors will be measured with the subject lying in a supine position on an examination table. Strength in the hip extensors will be measured with the subject leaning over an examination table in a prone position. All other muscle groups will be tested with the subject in a sitting position. All measurements will be taken bilaterally; the dominant side will be noted in the CRF. Three tests will be administered in an attempt to obtain two force values within approximately 15% of each other for each muscle group. The total force (in kg) will be recorded at the time of test

administration. The highest force value collected for each muscle group will be used for data analysis. The percent predicted values will be calculated after the testing using published normative data (Mathiowetz et al. 1985); (NIMS 1996); (Bohannon 1997); (Peters et al. 2011). Muscle strength and percent predicted values for each muscle group tested will be analyzed as secondary or tertiary endpoints (Section 7.6.4).

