8.5.4 Adverse Event Reporting

8.5.4.1 General

All AEs (i.e. any new or worsening in severity or frequency of a preexisting condition) with onset after the subject signs consent for study participation must be promptly documented on the CRF. The Principal Investigator is responsible for evaluating all AEs, obtaining supporting documents, and ensuring documentation of the event is adequate. Details of the AE must include severity, relationship to study drug, duration, and outcome.

All AEs will be collected from the time the subject signs the informed consent through 30 days following the last dose of study drug, or, if applicable, until the date the subject signs

the informed consent for the open-label extension study, UX001-CL302, whichever occurs sooner. In addition for those subjects choosing not to enroll in UX001-CL302, the Investigator should report any AE that occurs more than 30 days following the last dose of study drug that is believed to have a reasonable possibility of being associated with study drug.

AEs ongoing after the defined follow-up period stated in the paragraph above should have a comment in the source document by the Investigator that the event has recovered, recovered with sequelae, or stabilized.

8.5.4.2 Serious Adverse Events, Serious Adverse Drug Reactions, and Requirements for Immediate Reporting

Ultragenyx or its designee must be notified of the occurrence of any SAE that occurs during the reporting period within 24 hours of the Investigator, designee, or site personnel's knowledge of the event. SAEs will be reported by completing and submitting SAE report forms to Ultragenyx or designee.

Follow-up SAE information must be submitted in a timely manner as additional information becomes available. All SAEs regardless of relationship to study drug must be followed to resolution or stabilization if improvement is not expected.

All deaths, regardless of causality, occurring from signing of the informed consent through the defined follow-up period stated in Section 8.5.4.1 are to be reported as SAEs to Ultragenyx or its designee within 24 hours of knowledge.

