## 8.9 Safety Analyses

Analysis of safety will be performed on the safety analysis set. Blinded study data will be monitored on an ongoing basis by the clinical study team including the medical monitor and the clinical drug safety team to ensure patients' safety.

Safety will be evaluated by the incidence, frequency and severity of AEs and SAEs, including clinically significant changes from study baseline to scheduled time points in:

- Interval history
- Vital signs and weight
- Physical examination findings
- Clinical laboratory evaluations
- Suicidal ideation and behavior assessments
- Concomitant medications

All AEs will be coded using the Medical Dictionary for Regulatory Activities (MedDRA 17.1 or beyond). The incidence and frequency of treatment emergent AEs (occurred after the first dose of study drug) will be summarized by System Organ Class (SOC), Preferred Term (PT), severity, and relationship to treatment. The numbers (frequency) and incidence rates of AEs and SAEs will be summarized by treatment group. A by-subject listing will be provided

for those subjects who experience a SAE, including death, or experience an AE associated with early withdrawal from the study or study drug treatment. Each of these outputs will include tabulation by maximum severity for each SOC and preferred term. Summaries of AEs will be provided in descending order of frequency by SOC and preferred term.

Additional tables summarizing patient incidence (by preferred term) of the following will be generated:

- All AEs;
- SAEs;
- Treatment-related AEs;
- Treatment-related SAEs;
- AEs leading to the discontinuation of study drug or discontinuation of study;
- Deaths.

Separate outputs maybe be provided for subgroups defined by gender, and race (if feasible). Detailed listings for all AEs and listings and/or narratives will be provided for serious and significant AEs, deaths (with “on-study” deaths [deaths that occur before the end of safety follow-up period] identified).

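### Protocol 8.5.3 asks for relationship to study drug but defines all five categories by agent or procedure, so events caused by study tests can be rated Related

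*Protocol*

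**What the plan says.** Protocol 8.5.3 is headed as the relationship of adverse events to study drug, and its lead-in agrees: "The Investigator will assess the potential relationship of the AE to study drug using the following descriptions". The definitions that follow are wider. The highest category reads "This category applies to an AE that *is clearly related* to the investigational agent/procedure", and the lowest category on the Related side reads "This category applies to an AE that *may be related* to the investigational agent/procedure". The other three, including both Unrelated categories, use the same agent-or-procedure phrase. For regulatory reporting the five levels collapse to two: "AEs deemed as Definitely, Probably or Possibly Related will be considered Related".

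Protocol 8.5.4.1 describes one causality item: "Details of the AE must include severity, relationship to study drug, duration, and outcome". No procedure item is described.

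The rating is used in three places:

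- Protocol 7.3.3.1 (stopping rules) cites Section 8.5.3 and calls its three upper levels drug-related.
- SAP 8.9 summarises treatment-emergent events by relationship to treatment and lists tables of "Treatment-related AEs" and of treatment-related SAEs.
- SAP 8.9.1 repeats the related tables for the events to monitor.

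**The concern.** The definitions are what a rater applies, and here they ask a broader question than the heading and lead-in. Two investigators faced with the same test-related injury could both follow Section 8.5.3 and give opposite answers: Unrelated because the drug played no part, or Definitely Related because a procedure did.

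Two things are at stake. First, the treatment-related tables would mix two definitions. Both arms undergo the same tests, so procedure events in those tables would add to both arms and pull their relative comparison towards 1. Second, a serious injury during a study test could enter the evaluation and notification steps that Section 7.3.3.1 reserves for drug-related SAEs.

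**Working it through.** **Passages side by side**

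| Place | Cause being rated |
|---|---|
| Protocol 8.5.3, heading and lead-in | study drug |
| Protocol 8.5.3, all five definitions | agent or procedure |
| Protocol 8.5.4.1, recorded item | study drug |
| Protocol 8.5.1, suspected adverse reaction | the drug |
| Protocol 7.3.3.1, citing 8.5.3 | drug |
| SAP 8.9 and 8.9.1 | treatment |

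Only the definitions include procedures. The protocol separates the two causes elsewhere: Section 7.5.5.3 (interval history) names study procedures and study drug as distinct causes and excludes events due to either. A test-caused event therefore belongs on the adverse event form, where it must be rated. The product is an oral tablet, and Section 7.5 groups the strength and function tests under study procedures, so the tests are the natural referent of the word.

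**Exposure to the tests**

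Protocol 7.5.2.1 lists ten muscle groups (nine plus grip), measured on both sides, and says "Three tests will be administered in an attempt to obtain two force values within approximately 15% of each other for each muscle group". That gives 10 × 2 × 3 = 60 maximal efforts per visit, and 60 × 6 = 360 over the six post-dose visits (Weeks 8 to 48). The walk, sit-to-stand and arm-lift tests are added each time. This measures opportunity; it is not an event rate.

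**Illustration of the effect**

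The plan has no figure of its own to reproduce. The documents give no procedure-event rate and no expected drug-related rate for this trial, so every rate below is an assumption. Let p be the incidence of drug-related events in an arm. Let q be the incidence of procedure-caused events, equal in both arms, independent of p, and always rated Related.

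- Tabulated incidence = 1 − (1 − p)(1 − q)
- Difference between arms = (1 − q)(p for SA-ER − p for placebo)

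Example with p = 30% and 15%, q = 10%: 1 − 0.70 × 0.90 = 37.0% and 1 − 0.85 × 0.90 = 23.5%. The difference is 13.5 points and the ratio is 37.0/23.5 = 1.57.

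| q | SA-ER | Placebo | Difference (points) | Ratio |
|---|---|---|---|---|
| 0% | 30.0% | 15.0% | 15.0 | 2.00 |
| 5% | 33.5% | 19.3% | 14.3 | 1.74 |
| 10% | 37.0% | 23.5% | 13.5 | 1.57 |
| 20% | 44.0% | 32.0% | 12.0 | 1.38 |
| 30% | 51.0% | 40.5% | 10.5 | 1.26 |

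Other assumed drug-related rates behave alike. At q = 10%, 20% against 10% gives a ratio of 1.47 and a difference of 9.0 points; 40% against 20% gives 1.64 and 18.0 points. The direction is the same for any q above zero. The ratio moves more than the difference.

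**The case against.** The strongest reply is that the surrounding text points to drug only. The lead-in, Section 8.5.4.1, Section 7.3.3.1 and Section 8.5.1 all do so, and the adjective investigational can be read as qualifying procedure as well, which need not cover what Section 7.5.6 calls standard performance measures. This stands in part: the text permits the wider reading but does not require it. A reader might infer that test-caused events are in fact counted as treatment-related throughout the trial. No passage says that.

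The reach is also limited. The additional related tables in SAP 8.9 are by preferred term, so a fall or muscle soreness has its own row and does not dilute the gastrointestinal or liver rows. The events to monitor in SAP 8.9.1 are gastrointestinal terms and liver investigations, and the documents give no reason to expect study tests to cause many of these. All-causality AEs and SAEs are summarised by arm whatever the causality rating, and no between-arm test of adverse events is planned. These limits stand.

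Phase 2 gives little sign of a large effect. Protocol 5.2.3 says "Common TEAEs included headache, arthralgia, back pain, fatigue, diarrhea, influenza-like illness, musculoskeletal pain, myalgia", which includes terms that could plausibly follow maximal efforts. However, Section 5.2.4 lists the commonest treatment-related events as gastrointestinal events, headache and fatigue, with no musculoskeletal term. The causality wording used in Phase 2 is not shown, so this suggests a low q without proving it.

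Two further points count for less. Section 8.5.1 requires evidence of a link to the drug for expedited reporting, which is a partial safeguard, but Section 7.3.3.1 still relies on the 8.5.3 rating. The case report form and Study Reference Manual, which are not among the documents, might separate the two causes; even so, the protocol definitions would remain at odds with the item recorded.

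**Conclusion.** This is an internal inconsistency in an operative definition, and it should be corrected. As written, an investigator following Section 8.5.3 literally can rate a test-caused event as Related in either arm, and sites may differ in how they read it.

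The size is unknown. The ratios above rest wholly on assumed rates, on independence, and on every procedure-caused event being rated Related. They show direction and do not forecast this trial, so the documents do not support a conclusion that the drug-versus-placebo safety contrast is materially diluted.

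The effect is confined to descriptive summaries of related events, mainly overall and system-organ-class counts and musculoskeletal or injury terms, and to the classification of SAEs. The efficacy analyses and the all-causality safety tables are not affected.

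**What to change.** In Protocol 8.5.3, replace the agent-or-procedure phrase with *study drug* in all five definitions, so that they match the lead-in, Section 8.5.4.1 and the way Section 7.3.3.1 cites the scale. In SAP 8.9 and 8.9.1, add one sentence saying that treatment-related AE and SAE tables are built from the study-drug rating only.

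A separate yes/no item for relationship to a study procedure, with its own table, would be informative but is optional; the inconsistency is resolved without it.

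The cost is five wording edits in the protocol and a sentence in each SAP section. The downside is that related events already recorded under the present wording may need clarification from sites, chiefly those that could have arisen from a test. The optional item would add one case report form field and one table.
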